## 1.0 INTRODUCTION

Title	Pulmonary Functional Imaging for Radiation Treatment Planning for Lung Cancer
Short Title	SPECT/CT for Radiation in Lung Cancer
Phase	Pilot Study
Methodology	Single Arm Open-Label
Study Duration	2 years
Study Center(s)	University of Washington Medical Center
Objectives	To utilize SPECT/CT imaging with 99mTc-MAA and 99mTc-DTPA to accurately identify functional lung in patients receiving radiation treatment for lung cancer, and characterize tissue response to radiation. The long-term goal being to use functional imaging to guide radiation treatment planning, so functional lung tissue can be preferentially avoided, which will reduce radiation induced pulmonary toxicity allowing for increased dose delivery to the primary tumor.
Number of Subjects	20 evaluable subjects
Diagnosis and Main Inclusion Criteria	Patients diagnosed with non-metastatic lung cancers receiving radiation treatment, with impaired pulmonary function
Study Product, Dose, Route, Regimen	99mTc-MAA and 99mTc-DTPA SPECT/CT scans
Duration of administration	Drug administration will consist of 3 SPECT/CT scans with 99mTc-MAA and 99mTc-DTPA (one baseline scan which is standard of care, two follow up scans which are experimental and paid for by departmental research funds). The two experimental scans will be at mid-radiation treatment and approximately 3 months post-treatment.
Statistical Methodology	Outside the radiation field, normal lung tissue ventilation and perfusion over serial imaging will be assessed for stability using regression analysis, Pearson correlation, and Dice coefficient. Inside the radiation field, dose response curves will be developed for radiation dose versus changes in ventilation and perfusion. Gradient search algorithm in MIM 6.0. will be used to identify perfused and ventilated lung.

This document is a protocol for a human research study. This study is to be conducted according to US and international regulations, applicable government regulations and Institutional research policies and procedures.

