### 4.2 Endpoints

#### 4.2.1 Primary Endpoint

In this study, patients with lung cancer will undergo SPECT/CT imaging with  $^{99m}\text{Tc}$ -MAA and  $^{99m}\text{Tc}$ -DTPA at the time of radiation treatment planning. All image datasets will be imported into MIM 6.0, and fused with the radiation treatment planning CT and radiation plan. Lung tissue will be divided into tissue outside the radiation field (dose < 20th percentile of total lung dose) and tissue inside the radiation field (dose > 80th percentile of total lung dose). This process will be repeated for the mid-treatment scan and 3 months post-treatment scan. Lung tissue outside the radiation field will be compared on serial scans and their perfusion and ventilation quantified. There should be insignificant changes in perfusion and ventilation in >80% of lung tissue outside the radiation field. Lung tissue inside the radiation field will also be compared, and should yield significant differences in ventilation and perfusion between pre, mid, and post-treatment scans.

We will analyze the perfusion and ventilation data through multiple methods. Image sets from all 3 time points (before radiation, mid-radiation, 3-months post-radiation) will be fused using rigid registration. Regions of interest within the lung will be defined using automated and semi-automated methods, including simple thresholds and gradient-search algorithms. For each tracer, uptake value will be calculated for each voxel. For lung tissue outside the radiation field, summary statistics such as total regional uptake and mean regional uptake by lobe will be compared across the time points using parametric and non-parametric statistical testing. Voxel-based correlation, including Pearson linear and Spearman rank, will be performed to measure the stability of uptake between time points. Lastly, metrics of ventilation and perfusion volume overlap between time points will be estimated using the Dice coefficient.

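### The primary endpoint is judged by significant and insignificant changes that are tied to no single measure, unit, tracer, scan, test or level, and no listed method tests the first primary hypothesis

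*Combined protocol and SAP*

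**What the plan says.** The synopsis in section 1.0 describes a single-arm pilot with "20 evaluable subjects". Out-of-field ventilation and perfusion "will be assessed for stability using regression analysis, Pearson correlation, and Dice coefficient", and one segmentation tool, a gradient search, "will be used to identify perfused and ventilated lung".

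Section 4.2.1 opens its analysis paragraph with "We will analyze the perfusion and ventilation data through multiple methods". "Regions of interest within the lung will be defined using automated and semi-automated methods, including simple thresholds and gradient-search algorithms". For out-of-field lung, summaries such as "total regional uptake and mean regional uptake by lobe will be compared across the time points using parametric and non-parametric statistical testing". Pearson and Spearman voxel correlations and the Dice coefficient follow.

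The same section states two expectations. Change should be insignificant in more than 80% of out-of-field lung, and in-field lung should differ significantly between scans.

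Section 3.1 words the hypothesis differently. Change is smaller outside the field than inside. Out-of-field perfusion and ventilation stay constant or rise at both follow-up scans, and in-field values fall.

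The document gives no significance level, stability margin or rule for discordant results.

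**The concern.** The expectations in 4.2.1 read as pass/fail criteria, but they cannot be computed as written. The 80% could be a share of voxels, of lobes or of patients. The test and its level are not given. Nor is it said whether each tracer and each follow-up scan must pass separately. The parametric and non-parametric tests are planned for out-of-field lung only, and 4.2.1 names no test for the in-field expectation.

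Three further gaps bear on the same result:

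- The claim that change is smaller outside than inside is a direct contrast of two regions, and none of the listed methods makes it.
- A significant rise in out-of-field uptake would support section 3.1, which allows an increase, but would count against 4.2.1, which wants insignificant change.
- An insignificant result in 20 patients is not evidence of no change.

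At stake is whether the pilot can say that functional lung outside the field is stable. As the plan stands, the deciding analysis would be chosen after the data are seen.

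**Working it through.** There is no power calculation or error rate in the plan to reproduce; 20 is a bare target. The two-sided 0.05 level, the number of lobes, the correlations and the effect sizes below are assumptions.

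**1. Methods side by side (out-of-field stability)**

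| Method | Synopsis (1.0) | Section 4.2.1 |
|---|---|---|
| Regression | yes | no |
| Pearson | yes | yes |
| Dice | yes | yes |
| Spearman | no | yes |
| Parametric and non-parametric tests | no | yes |
| Gradient-search regions | yes | yes |
| Threshold regions | no | yes |

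**2. Number of out-of-field tests**

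Tracers × summaries × regions × follow-up scans against baseline × test types:

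- without lobes: 2 × 2 × 1 × 2 × 2 = 16
- with five lobes assumed and both summaries taken by lobe: 2 × 2 × 5 × 2 × 2 = 80

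Pearson, Spearman and Dice have no cut-off and are not counted.

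**3. Effect of the reading chosen**

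Simulation of 2,000 trials per scenario: 20 patients, 20 paired t-tests (2 tracers × 2 follow-up scans × 5 lobes), normal changes, equal correlation between comparisons. *Any* means at least one comparison is significant. *Tolerance* means more than 80% of comparisons are insignificant, that is, at most 3 of 20 significant.

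| Correlation | True change | Any | Tolerance met |
|---|---|---|---|
| 0 | none | 66% | 98% |
| 0.5 | none | 44% | 92% |
| 0.8 | none | 21% | 92% |
| 0 | −0.3 SD | 99% | 25% |
| 0.5 | −0.3 SD | 81% | 51% |
| 0.8 | −0.3 SD | 60% | 59% |

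A trial with no significant comparison always meets the tolerance. The share of trials in which both hold is therefore Any + Tolerance − 100%. At correlation 0.5 with a 0.3 SD fall this is 81 + 51 − 100 = 32%. In about a third of such trials the same data show a significant change under one reading and stability under the other.

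**4. What an insignificant result shows at n = 20**

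For one paired t-test with 19 degrees of freedom the critical value is 2.093 and the noncentrality is d√20.

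- d = 0.3: noncentrality 0.3 × 4.472 = 1.34, power 24.7%, so 75% of trials are insignificant.
- d = 0.5: noncentrality 0.5 × 4.472 = 2.24, power 56.5%, so about 44% are insignificant.

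The half-width of a 95% interval is 2.093 / √20 = 0.47 SD of the change. This is the precision that 20 patients give to any statement about stability.

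**5. Parametric against rank test**

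In the same simulation, replacing the t-test by the Wilcoxon test changed the tolerance verdict in about 0–12% of trials with normal data and 3–18% with skewed data (the skewed case run at correlation 0.5 only). The undefined unit and decision rule matter more than this choice.

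**The case against.** The strongest reply is that this is a 20-patient pilot that claims no error rate, and that 4.2.1 already contains a tolerance. Its wording on methods is also open-ended, and a synopsis is naturally shorter than the body. Pearson and Dice stand in both, and only regression is missing from 4.2.1.

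Much of this stands, and it rules out three stronger readings that a reader might infer.

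- *That stable lung would almost surely fail.* With 80 tests, 1 − 0.95^80 = 98% for at least one false signal. But 4.2.1 does not demand zero significant readings. If its tolerance is read as a share of tests, 80 × 0.05 = 4 expected false positives (5%) lie well inside the 20% allowed. Under independence the chance of 16 or more is about 2 in a million. Nor is five lobes given anywhere, and section 5.1.4.3 admits patients after lobectomy or pneumonectomy.
- *That a true hypothesis would usually be missed.* Section 3.1 joins its statements with *and*, so it reads as a conjunction of eight (2 regions × 2 tracers × 2 scans). At an assumed 80% each, independence gives 0.8^8 = 17%. The 80% is arbitrary, and readings from the same patients are correlated: the figure is about 42% at correlation 0.5 and 59% at 0.8.
- *That the choice of parametric or rank test decides the result.* Step 5 of the working shows that it is not the main driver.

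The reply does not make the tolerance computable or link it to any listed method. It also leaves the outside-against-inside comparison untested and lets non-significance stand for stability. Pilot status would excuse a purely descriptive plan, but this one states expectations in terms of significance.

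**Conclusion.** The point holds as a specification gap with practical consequences. The primary result is phrased as significance verdicts that the plan does not define, the synopsis and 4.2.1 differ in part, and sections 3.1 and 4.2.1 can disagree about an out-of-field increase.

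In the simulated case of a 0.3 SD fall everywhere at correlation 0.5, about 81% of trials show some significant change and about half still meet the 80% tolerance. One paired test at 20 patients misses a 0.5 SD change about 44% of the time. These figures rest on the assumed level, five lobes, normal changes, equal correlation and a tolerance read as a share of comparisons. They illustrate how far the reading matters and do not predict this trial's results. The amendment should be made, but the design, sample size and scans need not change because of this point.

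**What to change.** In section 4.2.1:

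1. Name one primary patient-level quantity that matches section 3.1. An example is the within-patient difference between out-of-field and in-field change in mean uptake from baseline to the 3-month scan, for one designated tracer. Analyse it by one paired method and report it with a confidence interval.
2. Judge out-of-field stability by whether the interval for the out-of-field change lies within a prespecified margin, not by non-significance. State whether an increase counts as stable, so that 3.1 and 4.2.1 agree. Set the margin knowing that the 95% interval at 20 patients is about ±0.47 SD of the change.
3. Replace the 80% criterion, or define its unit, measure, test and level.
4. Report the other tracer, the mid-treatment scan, lobe summaries, correlations and Dice as supportive estimates with intervals and no significance verdicts.
5. Make the statistical methodology row of the synopsis match, including regression and the method for defining regions.

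Cost: the protocol's endpoint wording must be amended, and the sponsor must choose a tracer and justify a margin. The other measures can no longer carry the primary conclusion. No patients or scans are added.

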## 3.0 STUDY OBJECTIVES

### 3.1 Primary Objective

To utilize SPECT/CT imaging with  $^{99m}\text{Tc}$ -MAA and  $^{99m}\text{Tc}$ -DTPA to identify functional lung on serial imaging in patients receiving radiation treatment for lung cancer, as well as to characterize reproducibility of perfusion and ventilation in non-irradiated lung tissue.

Hypothesis: For lung tissue outside the radiation field, perfusion and ventilation as defined by SPECT/CT imaging with  $^{99m}\text{Tc}$ -MAA and  $^{99m}\text{Tc}$ -DTPA will exhibit smaller changes over time than tissue inside the radiation field. Compared to the pre-radiation scan, lung tissue receiving radiation dose below the 20th percentile of total lung will have perfusion and ventilation that remain constant or increase at the mid-radiation treatment scan and 3-months post-treatment scans. By contrast, lung tissue receiving radiation dose above the 80th percentile of total lung will have perfusion and ventilation that decrease at the mid-radiation treatment scans and 3-months post-treatment scans.

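### Voxel-level Pearson and Spearman cannot measure stability of uptake level, and neither they nor the planned lobar tests give the share of stable out-of-field lung that the primary endpoint refers to

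*Combined protocol and SAP*

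**What the plan says.** Section 3.1 sets out to "characterize reproducibility of perfusion and ventilation in non-irradiated lung tissue". Its hypothesis is directional and concerns level: compared with the pre-radiation scan, low-dose lung "will have perfusion and ventilation that remain constant or increase at the mid-radiation treatment scan", and likewise at three months.

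Section 4.2.1 defines out-of-field lung as tissue below the 20th percentile of lung dose and expects more than 80% of it to show no significant change. It then lists several analyses:

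- Level by lobe: "total regional uptake and mean regional uptake by lobe will be compared across the time points using parametric and non-parametric statistical testing".
- Voxel association: "Voxel-based correlation, including Pearson linear and Spearman rank, will be performed to measure the stability of uptake between time points".
- Overlap: "metrics of ventilation and perfusion volume overlap between time points will be estimated using the Dice coefficient". The regions come from automated and semi-automated methods, "including simple thresholds and gradient-search algorithms".

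The synopsis in section 1.0 is shorter. Normal lung outside the field "will be assessed for stability using regression analysis, Pearson correlation, and Dice coefficient", and gradient search is the only segmentation method it names. It omits the lobar comparison and does not say what is regressed on what.

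The plan does not say which measure decides the primary endpoint, what size of change counts as insignificant, whether thresholds are absolute or relative, or whether voxel uptake is normalised.

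**The concern.** The hypothesis asks whether uptake stayed at its level. The statistics given the job of measuring stability at voxel level ask whether voxels kept their order, or their linear relation, between scans. These are different questions, and the first can fail while the second is answered perfectly.

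Both coefficients also depend on how widely uptake varies within the region. Patients qualify through impaired lung function, and section 2.1 describes the underlying lung disease as often patchy. A high coefficient may therefore partly reflect the disease pattern rather than good repeatability.

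Section 2.4 ties the benefit of the study to finding lung that stays ventilated and perfused. If high r and high Dice were reported as showing this, later planning on the baseline scan would rest on measures that do not register an even change in level.

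**Working it through.** The documents give no figure to reproduce here: there is no cut-off for r or Dice and no basis for the 20 subjects. The checks below use algebra and a simulation. Every voxel SD, error SD and voxel distribution is assumed.

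**1. Even change in level.** Let follow-up uptake be Y = a + bX with b > 0. Then Pearson = Spearman = 1 whatever a and b are. This was checked on 20,000 simulated voxels (gamma, shape 4, scale 25):

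- Even losses of 10% to 50%, no noise: Pearson 1.000, Spearman 1.000.
- With 10% log-normal voxel noise: 0.976 and 0.980 at every loss, the same as with no loss.
- Mean ratio and regression slope, no noise: 0.90, 0.80, 0.70 and 0.50 for losses of 10%, 20%, 30% and 50%. These do register the loss.

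**2. Dependence on spread.** Suppose there is no true change and independent error of SD 10 on each scan. Then r = SD_true² / (SD_true² + 10²).

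| True voxel SD | r | SD of voxel differences |
|---|---|---|
| 10 | 100/200 = 0.50 | √(10² + 10²) = 14.1 |
| 20 | 400/500 = 0.80 | 14.1 |
| 30 | 900/1000 = 0.90 | 14.1 |

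Repeatability is identical in the three rows, and only r moves. The regression slope of follow-up on baseline has the same expected values here, so a slope below 1 does not by itself separate loss from noise.

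**3. Dice.** For an even loss without noise, with thresholds at 25%, 40% and 50% of near-maximum (99.9th percentile):

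- Threshold relative to each scan: 1.000 at any loss.
- Threshold fixed at the baseline value: 0.822, 0.614, 0.507 at 20% loss; 0.289, 0.057, 0.021 at 50% loss.

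The relative result needs the reference maximum to fall by the same factor as the region. Gradient search was not simulated. If a share p of the region is functional on each of two unrelated scans, chance Dice is 2p²/(2p) = p. With p = 0.80 (assumed) that is 0.80.

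**4. The share of tissue.** After an even 20% loss without noise, no voxel lies within any limit smaller than 20%, yet r = 1. Conversely, if half the voxels of a lobe rise 20% and half fall 20% from equal baselines, the lobar mean is unchanged, and again no voxel lies within such a limit. Neither statistic yields the share that the 80% statement needs.

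**5. Lobar tests.** With 20 subjects and a two-sided 5% paired t-test, power to detect a 10% mean loss is 0.99, 0.57 and 0.29 if the between-patient SD of percent change is 10, 20 and 30 points (assumed). At the larger SDs, a non-significant result would often accompany a real loss.

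**6. Lin's concordance as a substitute.** For Y = fX and the gamma above (mean² = 4 × variance), it equals 2f / (1 + f² + 4(1 − f)²). At f = 0.8 this is 1.6/1.80 = 0.89. At f = 1.2 it is 2.4/2.60 = 0.92. It therefore marks down a rise, which the hypothesis counts as support, and it too depends on spread.

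**The case against.** The strongest reply is that level is already examined. Section 4.2.1 announces multiple methods, and the sentence just before the one on correlation compares total and mean uptake by lobe across time points. An even 20% fall would appear there as a ratio of 0.80, provided uptake is not normalised to a total that falls with it. The synopsis adds regression, whose slope would also respond. Correlation and Dice suit the other half of the primary objective, which is to identify functional lung on serial scans.

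This stands. A reader might infer that the primary endpoint is blind to loss of uptake, or that evenly declining lung would pass as stable. The documents do not support that, because two level-sensitive analyses are named. A reader might also infer that Dice is blind to level. That holds only for thresholds that scale with each scan, and the plan leaves the choice open. Nor do the documents plan to compare r between patients or give the functional share of the region. The 80% in section 4.2.1 is the share expected not to change.

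The reply does not make correlation a measure of level, turn a non-significant lobar test into evidence of stability, or supply a tissue share. This is a single-arm pilot, so clarity about what each statistic shows matters more than formal error control.

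**Conclusion.** The point holds in a limited form. Pearson and Spearman do not measure stability of uptake level, contrary to what section 4.2.1 says of them. That part is algebra and needs no assumption. The dependence on spread is also general, but the values 0.50, 0.80 and 0.90 rest on assumed SDs. Blindness of Dice to an even loss is conditional on relative thresholds.

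The lobar comparison and regression respond to level, so an even loss need not go unseen. What is missing is a designated deciding measure, a limit of change, and any statistic that gives the share of out-of-field tissue within that limit. This should be corrected before analysis. It does not put the data collection in question.

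**What to change.** In section 4.2.1 and the synopsis:

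- Describe Pearson and Spearman as measures of spatial pattern, and Dice as a measure of overlap.
- State one common uptake scale for all three scans, including any normalisation. Without it, level differences may also reflect the amount of tracer delivered.
- On that scale, for each patient and tracer, report the signed mean difference or percent change from baseline in out-of-field lung with its confidence interval. Add the within-patient SD of voxel differences, labelled as scan error plus real change, because the scans span radiation and are not pure repeats.
- Report the share of out-of-field voxels or subregions whose change lies within a prespecified limit, counting increases as the hypothesis does. Let this and the signed change, together with the lobar comparison, decide stability.
- Compute Dice with a threshold fixed on the baseline scan on the same scale, and show it beside its chance value.
- Treat Lin's concordance as optional and secondary.

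The cost is some wording and a little extra analysis of images already planned. The investigators must choose and justify the scale and the limit in advance. The resulting figures may look less favourable than r and Dice.

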### 3.2 Secondary Objective

a) To estimate the dose response relationship on multiple spatial scales (global lung, regional lung, lung image voxel) between radiation dose and changes in lung ventilation and perfusion, both acutely (mid-radiation treatment) and long term (3 months post-treatment), using SPECT/CT imaging with  $^{99m}\text{Tc}$ -MAA and  $^{99m}\text{Tc}$ -DTPA.

Hypothesis: Compared to the current models of radiation dose response for lung tissue, using CT in addition to SPECT imaging acquired in the radiation treatment position, a more accurate regional dose response relationship between radiation dose and changes in lung function can be generated with superior volumetric and quantitative data.

b) To estimate the degree of radiation response in lung tissue with varying levels of function (i.e. compare radiation dose response of well ventilated and well perfused tissue against lung tissue with poor perfusion and ventilation). This may establish a threshold of lung tissue that would be “safe” to treat without significantly affecting lung function.

Hypothesis: Well-perfused and ventilated lung tissue has a different radiation dose response curve than lung tissue that receives poor ventilation and perfusion (upper quartile versus lower quartile of perfused and ventilated tissue image intensity distributions). The dose-response relationship can be modeled either as a linear or sigmoid function.

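### Dice overlap is planned as a measure of out-of-field stability with no chance reference, although its chance value rises with the share of lung called functional

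*Combined protocol and SAP*

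**What the plan says.** The synopsis (1.0, Statistical Methodology) states that ventilation and perfusion of normal lung outside the field will be "assessed for stability using regression analysis, Pearson correlation, and Dice coefficient". Section 4.2.1 closes its list of analyses with the statement that "metrics of ventilation and perfusion volume overlap between time points will be estimated using the Dice coefficient". Neither place gives a chance value, a benchmark or a chance-corrected index.

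The masks that enter Dice are described only in general terms. Section 4.2.1 says: "Regions of interest within the lung will be defined using automated and semi-automated methods, including simple thresholds and gradient-search algorithms". The synopsis adds that a gradient search algorithm "will be used to identify perfused and ventilated lung". No cut-off is stated, and no fixed fraction of lung is set for the overlap analysis. A fixed split does appear in 3.2(b), "upper quartile versus lower quartile of perfused and ventilated tissue image intensity distributions", but it serves the secondary aim and is not stated for Dice.

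Two other parts of 4.2.1 bear on the point. The same paragraph plans that "Voxel-based correlation, including Pearson linear and Spearman rank, will be performed to measure the stability of uptake between time points". The only numeric stability criterion is "There should be insignificant changes in perfusion and ventilation in >80% of lung tissue outside the radiation field", and it is not tied to Dice.

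**The concern.** Dice is computed inside a bounded region, here lung below the 20th dose percentile. When most of such a region is called functional on both scans, the two masks must overlap a good deal wherever the functional voxels lie. A raw Dice that looks high may then say little about whether the functional tissue stayed in place.

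The functional share can be expected to vary in this trial. Section 5.1.4 admits patients through abnormal lung function tests, previous lung irradiation, previous resection, COPD or emphysema, or oxygen use, and 2.1 describes the underlying lung disease as often uneven. There are two tracers and more than one segmentation method.

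What is at stake is the reading of the one listed measure that asks directly whether the functional volume remains in the same location. That question lies behind the benefit described in 2.4: finding functional lung reliably enough to protect it.

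**Working it through.** **Inputs.** The metric and its role come from 1.0 and 4.2.1. The documents give no Dice target, chance value or functional share, so there is no figure of the plan's own to reproduce. The shares below are assumptions.

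**Chance value.** Let masks A and B cover shares p1 and p2 of a region of volume V. Dice = 2|A∩B| / (|A|+|B|). If the maps are spatially unrelated, the expected overlap is p1·p2·V, so

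chance Dice ≈ 2·p1·p2 / (p1+p2).

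With p1 = p2 = p this is 2p²/(2p) = p. With unequal shares it is their harmonic mean: 0.8 and 0.6 give 0.96/1.4 = 0.686; 0.5 and 0.25 give 0.25/0.75 = 0.333.

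**Simulation check.** Unrelated maps on 40×40×40 grids, 60 pairs per share:

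| p (both scans) | mean Dice, independent voxels | mean Dice, smoothed maps |
|---|---|---|
| 0.25 | 0.250 | 0.261 |
| 0.50 | 0.500 | 0.496 |
| 0.70 | 0.700 | 0.700 |
| 0.80 | 0.800 | 0.803 |

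Spatial smoothness, which real SPECT maps have, leaves the mean almost unchanged.

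**Chance correction.** Let p11 be the share of the region that is functional on both scans. Cohen's kappa is 2(p11 − p1·p2) / (p1 + p2 − 2·p1·p2). Dividing numerator and denominator by (p1+p2) gives

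kappa = (Dice − chance Dice) / (1 − chance Dice),

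which for equal shares is (Dice − p)/(1 − p). For an observed Dice of 0.85:

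- p = 0.3: 0.55/0.70 = 0.79
- p = 0.5: 0.35/0.50 = 0.70
- p = 0.7: 0.15/0.30 = 0.50
- p = 0.8: 0.05/0.20 = 0.25

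An observed Dice of 0.80 at p = 0.8 gives kappa 0, exactly what unrelated maps produce on average.

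**Same agreement, different share.** One million simulated voxel pairs with a true correlation of 0.5, thresholded to a common share:

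| p | Dice | (Dice − p)/(1 − p) |
|---|---|---|
| 0.25 | 0.481 | 0.308 |
| 0.50 | 0.666 | 0.332 |
| 0.80 | 0.859 | 0.296 |

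The underlying agreement is identical in the three rows. Raw Dice moves from 0.48 to 0.86, while the corrected value stays near 0.30 to 0.33.

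**The case against.** The strongest reply is that nothing in the plan turns on Dice. It comes last in the list, is to be estimated and not tested, and has no threshold. Pearson and Spearman voxel correlations sit in the same paragraph and have a null of 0, so unrelated maps would show up as correlations near zero whatever the Dice. This stands and limits the point to interpretation. It does not remove it: the correlations describe agreement in uptake, not overlap of the segmented volume, and they do not tell a reader what a given Dice means.

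A second reply is that independence is a weak reference for co-registered scans of the same lung, where the interest is in how close agreement comes to complete. That is fair. A chance value supplies the floor, not the target, but without the floor a Dice of 0.80 cannot be placed.

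Third, kappa is no cure-all. It also depends on prevalence: with both shares at 0.9, a Dice of 0.95 gives (0.95 − 0.90)/0.10 = 0.50. Resting the stability statement on kappa alone would therefore be a debatable preference.

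A reader might also infer that the plan will compare Dice between patients, tracers, thresholds, or inside versus outside the field. The documents state no such comparison. The synopsis assigns Dice to lung outside the field, and 4.2.1 uses it between time points; 4.2.2 says only that in-field images are processed in a similar way. Non-comparability is thus a caution for any such use, not a fault in a stated analysis.

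**Conclusion.** The point holds as a gap in the interpretation of one component of the primary endpoint. Raw Dice has a chance value that depends on the functional share, the plan leaves that share free, and it gives no reference. The formula is general; its size here rests on assumed shares. Over equal shares of 0.3 to 0.8, a Dice of 0.85 ranges from substantial agreement beyond chance (kappa 0.79) to little (0.25). If the masks cover a small part of the region, the effect is minor.

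Two stronger readings are not supported. A reader might infer that the primary endpoint as a whole is undermined; it is not, because the correlations are planned alongside and the only numeric criterion is separate from Dice. A reader might also extend the example and conclude that a Dice of 0.85 falls below chance when 90% of the region is functional on both scans. That value cannot occur: the masks must share at least 80% of the region, so the lowest possible Dice is 0.80/0.90 = 0.889.

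**What to change.** In 4.2.1, require that every Dice value, per patient, tracer and scan pair, is accompanied by:

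- the functional share at each scan, p1 and p2, within the region where Dice is computed;
- the chance Dice, 2·p1·p2/(p1+p2);
- kappa within that same region.

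State that Dice counts as evidence of stability only relative to its chance value and together with the voxel correlations. If Dice is compared across patients, tracers, segmentation methods or regions, show the chance-corrected value too, with a note that kappa also depends on prevalence. Align the synopsis wording.

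Dice at a matched percentile share on each scan may be added as a supplement. It holds the chance value constant, but it cannot show gain or loss of functional volume, so it should not replace the main overlap analysis.

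The cost is a few extra reported columns from the existing masks. The optional matched-share analysis needs new masks from one re-threshold of the existing voxel data. No further scans, patients or visits are needed. The overlap results may look less favourable.
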